Efficacy Study of the LARA Wheelchair System for Subacute Stroke Patients

NCT 02830893

Standard Operating Procedures

February 28, 2018

Table of Content

- 1. Background and Population
- 2. Inclusion and Exclusion Criteria
- 3. Methods
- 4. Timeline of the Study
- 5. Table of Clinical Testing
- 6. List of Clinical Tests
- 7. Daily Study Procedures
- 8. Statistical Considerations

Background

We will recruit 44 individuals with an acute or subacute stroke (3 days to 30 days post stroke) to participate in this randomized controlled trial at UCI ARU and Rancho Los Amigos National Rehabilitation Center. These individuals will have an acute or subacute stroke with arm/ hand weakness defined as a score of less than 50 (out of 66) on the arm motor scale of the Fugl-Meyer Assessment.

Inclusion Criteria:

- 1. History of stroke affecting the arm, at least 3 days to 30 days prior to enrollment
- 2. Age 18 to 80 years of age
- 3. Upper extremity weakness, defined as a score of less than 50 (out of 66) on the arm motor scale of the Fugl-Meyer Assessment

Exclusion Criteria:

- 1. Moderate to severe pain in the stroke-affected upper extremity (score >6 on 10-point visual analog pain scale), at rest or increased when attempting to use LARA
- 2. Severe tone at the affected upper extremity (score >4 on the Ashworth Spasticity Scale)
- 3. Severe aphasia (score of 2 or higher on the NIH stroke scale question 9)
- 4. Deficits in vision, language, attention, or other cognitive functions severe enough to interfere with using LARA
- 5. Currently pregnant
- 6. Difficulty in understanding or complying with instructions given by the experimenter
- 7. Inability to perform the experimental task that will be studied

Methods:

The primary outcome measure will be the Upper Extremity Fugl-Meyer Score to assess motor impairment in the affected arm. Secondary outcome measures will be Box and Blocks Test, Modified Ashworth Scale of Spasticity to measure spasticity of the shoulder, elbow, wrist and hand, Visual Analog Pain scale to assess pain, NIH Stroke Scale, mini mental state exam to assess cognitive function and the Borg scale to access their perceived exertion levels. We will perform testing at three separate evaluations: At the initial baseline visit, 3-weeks post therapy or the day before discharge if sooner, and 3-month follow up. The end point of the study will be the 3-month after baseline evaluation.

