10	2			8	A: LARA or B: Tabletop exercise program
11	2			9	A: LARA or B: Tabletop exercise program
12	2			10	A: LARA or B: Tabletop exercise program
13	3			11	A: LARA or B: Tabletop exercise program
14	3			12	A: LARA or B: Tabletop exercise program
15	3			13	A: LARA or B: Tabletop exercise program
16	3			14	A: LARA or B: Tabletop exercise program
17	3			15	A: LARA or B: Tabletop exercise program
18	3	2	All clinical outcomes		
19	13	3	All clinical outcomes: Follow-up		

Table of Clinical Testing

	Screen	Evaluation #1	Evaluation #2	Evaluation #3
		(Baseline)	(Post therapy)	(3-month follow up)
Consent Form	Х			
HIPAA wavier form	Х			
Photography consent	X			
Medical History/ Health Status Questionnaire/ Rehab History overall	Х			
NIHSS	X	X	X	X
Box and Blocks Test		X	X	X
Mini Mental State Exam		X	X	Х
Modified Rankin Scale		X	X	Х
Motor sections of Fugl- Meyer	Х	Х	Х	Х
Action Research Arm Test		Х	Х	Х
Motor Activity Log		X	Х	X
10-meter walk		X	Х	X
Grip Strength		X	X	X
AROM & PROM at shoulder and elbow		Х	Х	Х
Geriatric Depression Scale		Х	Х	Х
Modified Ashworth Scale of Spasticity (Shoulder, Elbow, Wrist, Finger)	Х	Х	Х	Х
Visual Analog of Pain Scale	Х	Х	Х	Х
IMI	Х	X	X	X
Stipend	X	X	X	Х

List of Clinical Tests

- 1. Upper Extremity Fugl-Meyer Motor Score study primary outcome measure
- 2. Box and Blocks Test
- 3. Motor Activity Log
- 4. Action Research Arm Test
- 5. Active and passive range of motion at the shoulder and elbow
- 6. Modified Ashworth Spasticity Scale
- 7. Visual Analog Pain Scale
- 8. 10-meter walk test
- 9. NIH stroke scale
- 10. Mini-Mental State Examination
- 11. Geriatric Depression Scale
- 12. Modified Rankin Scale Score
- 13. Grip Strength

Total Score	/66	
Proximal	/36	Subject ID
Wrist/Hand	[ 24	Date
Coordination/Speed	/ 6	Visit #
Affected side (R or L) _	 	

FUGL-MEYER ARM MOTOR ASSESSMENT Remember to score best, not first, patient performance

Pr	oximal				
LF	Reflexes				
Biceps or finger flexor reflex			0 [no reflex]	2 [reflex elicitable]	
2.	Triceps reflex		0 [no reflex]	2 [reflex elicitable]	
Ш	Flexor Synergy				
		cted to voluntarily bring affect lder abducted 90°/externally	ed forearm fully supinated to rotated/retracted/elevated.	ear of the affected side,	
3.	Shoulder girdle retraction	0 [not done at all]	1 [partly done]	2 [faultless]	
4.	Shoulder girdle elevation	0 [not done at all]	1 [partly done]	2 [faultless]	
5.	Shoulder abduction	0 [not done at all]	1 [partly done]	2 [faultless]	

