1a. Level of Consciousness Must choose a response.	0=Alert; keenly responsive	
	1=Not alert; but arousable by minor stimulation	
	2=Requires repeated or painful stimuli to attend	
	3=Reflex motor, flaccid, or areflexic	
1b. LOC Questions Ask pt his age & the month; must	0=Both correct	
be correct. Tube, dysarthria, foreign lang. barrier=1.	1=One correct	
1.1000	2=Neither correct; aphasia or stupor=2	
1c. LOC CommandsAsk pt to open & close eyes,	0=Both correct; full credit if incomplete 2° weak	
then grip & release non-paretic hand. Can use	1=One correct	
different 1-step command or pantomime instructions.	2=Neither correct	
2. Best GazeHorizontal EOM only, voluntary or	0=Normal	
Doll's. Conjugate deviation which can be	1=Partial gaze palsy; abnl gaze in 1 or both eyes	
overcome=1. Isolated CN palsy=1.	2=Forced deviation or total gaze paresis not overcome by Doll's	
3. Visual FieldUse visual threat if nec. If monocular,	0=No visual loss	
score per field of remaining eye. Quadrantanopia=1.	1=Partial hemianopia, quadrantanopia, or extinction.	
score per field of remaining eye. Quadramanopia-1.	2=Complete hemianopia	
	3=Bilateral hemianopia or any blindness, incl/ctxcl	
4. Facial PalsyIf stuporous, check symmetry of	0=Normal	
grimace to pain.	1=Minor paralysis, flattened NLF, asym smile	
griniace to pain.	2=Partial paralysis (paralysis of lower face)	
	3=Complete paralysis (upper & lower face)	
5. Motor Arm* extend pt's arm 90 deg (sitting) or 45	0=No drift for 10 sec	Paretic arm
deg (supine); watch for 10 sec. Use pantomime or	1=Drifts before 10 sec but does not hit bed	is
voice urgency but not pain. Begin w/stronger arm.	2=Some effort vs. gravity, can't maintain postn	L R
Circle paretic arm in score box.	3=No effort vs. gravity	
1	4=No movement (score 3 if any mvmt in extremity)	
Other Arm*For brainstem stroke.	0-4, use same scale as above. Circle L & R.	
6. Motor Leg*Place leg at 30 deg (always supine);	0-4, use same scale as above	L R
watch for 5 sec.	Circle paretic leg in score box.	
Other Leg*For brainstem stroke.	0-4, use same scale as above. Circle L & R.	
7. Limb Ataxia*OU open, in good vis field. Only	0=No ataxia	
score if o/o proportion to any weakness. Score 0 if	1=Ataxia in 1 limb (upper ext or lower ext;; specify limb in score	
pt can't understand or is hemiplegic. If blind, pt to	box)	
touch nose after extending arm.	2=Ataxia in upper ext and lower ext	
8. SensoryUse pin; only score losses related to the	0=Normal	

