stroke. Can assess by grimace or withdrawal if pt	1=Mild-mod sensory loss, less sharp on affected side, pt aware of	
obtunded. Score 2 only if pt clearly comprehends	being touched	
thus aphasics/stupor usually=1.	2=Severe total sensory loss, unaware of touch; unresponsive=2, bilat	
1 1 3	sens loss(brnstem)=2	
9. Best LanguageDescribe cookie thief, name	0=Normal	
pictures, read sentences; can use stereognosis,	1=Mild-mod aphasia	
repetition, or writing. Score=3 only if pt mute &	2=Severe aphasia; great need for guessing & inference by examiner;	
follows no 1 step commands.	lim'd info exchanged. Examiner carries burden of	
	communication.	
	3=Mute, global aphasia, coma	
10. Dysarthria*Have patient read from list of words;	0=Normal	
can rate speech w/severe aphasia. Score=X only if	1=Mild-mod; pt slurs but can be understood	
patient intubated or has other barrier.	2=Severe; unintelligible. Mute/anarthric=2	
11. Extinction & Inattentionsevere vis loss + normal	0=Normal or none detectable	
sens=0; aphasia but attending well bilat'ly=0. Vis	1=Inattention or extinction on DSS in any of vis, auditory, sens,	
neglect or anosognosia =abnl.	spatial, or personal	
	2=Profound in > 1 modality	

Subject ID:
Date:
Exam #
Mini-Mental State Examination CMMSE)
ORIENTATION-onepointforeachanswer
"What is the date to day? (year) (date) (month) (day) (season)?"(5) _ "Where are we? (state) (county) (town) (hospital) (floor)?" (5)
REGISTRATION – score 1,2,3 points according to how many are repeated on first try (Apple, piano, green)
Name three objects: Give the patient one second to say each.
Ask the patient to: repeat all three after you have said them. Repeat them until the patient learns all three. (3)
ATTENTION AND CALCULATION - one point for each correct subtraction
Ask the patient to: begin from 100 and count backwards by 7. Stop after 5 answers. (93, 86, 79, 72, 65) or Spell WORLD backwards (5)
RECALL-onepointforeachcorrectanswer
Ask the patient to: name the three objects from above. (3)
LANGUAGE
Ask the patient to: identify and name a pencil and a watch. (2)
Ask the patient to: repeat the phrase "No ifs, ands, or buts." (1)

Ask the patient to: "Take a paper in your right hand, fold it in half, and put it on the floor
(1 point for each task completed properly)(3)
Ask the patient to: read and obey the following: (1)

Close your eyes

Ask the patient to: write a sentence. (1)	
Ask the patient to: copy a complex diagram of two interlocking pentagons. (1)	

TOTAL:_____/30

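### The MMSE form tells everyone to use the right hand and scores physical completion, so part of any change in this cognitive outcome could reflect hand recovery

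*Combined protocol and SAP*

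**What the plan says.** The Methods section lists among the secondary outcomes the "mini mental state exam to assess cognitive function". The Table of Clinical Testing schedules it at baseline, post therapy and the 3-month follow-up.

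The MMSE form, under List of Clinical Tests, contains the command "Take a paper in your right hand, fold it in half, and put it on the floor", scored "1 point for each task completed properly)(3" points in all. Two later items also need a hand: writing a sentence and copying interlocking pentagons, at 1 point each. The form gives no alternative hand, no credit for weakness and no rule for an item that cannot be attempted.

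The Inclusion Criteria require "Upper extremity weakness, defined as a score of less than 50 (out of 66) on the arm motor scale of the Fugl-Meyer Assessment", with no lower limit and no restriction on side. The Fugl-Meyer form records the affected side as right or left.

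The NIH Stroke Scale form in the same document handles this differently. Item 1c asks the patient to open and close the eyes, "then grip & release non-paretic hand", and gives full credit when weakness is the reason the act is incomplete.

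Statistical Considerations applies repeated-measures ANOVA to each outcome measure and hypothesises a greater reduction in motor impairment with LARA. It states no cognitive hypothesis, does not mention the MMSE by name, and plans no analysis by affected side.

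**The concern.** A cognitive measure should not move when only the arm changes. Here the form names a fixed hand in a trial where a weak arm is an entry criterion. If that hand is the paretic one, a participant who understands the command perfectly can still lose points, then regain them as the arm recovers.

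The trial expects the arm to recover more with LARA. Any such artefact would therefore tend to favour LARA on an outcome described as cognitive. An imbalance of affected side between the groups could also shift baseline means. With no written rule, raters at the two sites could handle the item differently.

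**Working it through.** **Inputs from the document.** MMSE item points come from the form. The sample size is 44 in two groups (Background; Methods).

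**Inputs that are assumed.** The document gives no allocation ratio, share with right-sided paresis, recovery rate of the paper task, MMSE standard deviation, alpha or power. I assume 22 per group, 30-70% right-paretic, 10-30 percentage points more LARA participants regaining the task, an SD of 2-5 points, two-sided alpha 0.05 and 80% power.

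**1. The printed maximum.** Orientation 5 + 5, registration 3, attention 5, recall 3, naming 2, repetition 1, paper command 3, reading 1, sentence 1, pentagons 1: total 30, as printed.

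**2. Points at stake.**
- The wording ties only the first step, taking the paper, to the right hand: 1/30 = 3.3%.
- The whole command, if folding and placing also fail or the rater insists on the right hand: 3/30 = 10%. An otherwise perfect score would then be 27.
- Sentence and pentagons add 2 if the paretic hand is also the writing hand: 5/30 = 16.7%, leaving 25. Neither item names a hand, so this part follows handedness, not the right side.

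**3. Spurious difference between groups.** Difference = share right-paretic × gap in regaining the task × points at stake.
- 1 point: 0.3 × 0.1 × 1 = 0.03 to 0.7 × 0.3 × 1 = 0.21.
- 3 points: 0.3 × 0.1 × 3 = 0.09 to 0.7 × 0.3 × 3 = 0.63.
- 5 points, as an outer bound that requires every affected participant to write with the paretic hand and to regain all five points: 0.15 to 1.05.

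**4. Baseline imbalance.** Suppose one group of 22 has four more right-paretic participants and all four fail. Its mean is lower by 4 × 1/22 = 0.18 points, or by 4 × 3/22 = 0.55 if the whole command is lost. This is an offset at baseline; it is not in itself a difference in change.

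**5. Comparison with what the trial can detect.** Detectable difference = (1.96 + 0.84) × SD × √(2/22).
- SD 2: 1.69 points.
- SD 5: 4.22 points.

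The ranges for 1 and 3 points lie below this.

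**6. Effect on false positives.** By the normal approximation, a shift of 0.30 points with SD 3 raises the two-sided error rate from 5% to 6.3%. The least favourable combination for the 3-point case, 0.63 points with SD 2, raises it to 18.1%. With 0.15 points and SD 5 it is 5.1%.

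**The case against.** The strongest case on the other side is that the effect is smaller and less certain than it first appears. Much of that case stands.

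- A reader might infer that every right-paretic participant stands to lose 5 of 30 points. The form does not support this. It names the right hand once. Folding, placing, writing and copying name no hand, and nothing bars the sound hand. Someone who folds and places the paper with the left hand loses 1 point. Losing 3 takes a strict rater or real difficulty with the later steps; losing 5 also requires that the paretic hand be the writing hand.
- A reader might infer that only right-sided paresis matters. The document does not support that either. Folding often uses both hands, writing and copying depend on handedness, and the MMSE form does not record the writing hand.
- A Fugl-Meyer score below 50 includes people who can still pick up and fold paper, so not all right-paretic participants lose points.
- Raters may have been trained to score comprehension. The document does not say, and the absence of a printed allowance does not prove that points will be deducted.
- The MMSE is secondary, and no cognitive claim is hypothesised.

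These points limit the size and widen the group who may be affected. They do not remove the problem: the printed instruction names the right hand, the printed scoring is by completion, and the NIH Stroke Scale form shows that the allowance can be made in a command item.

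**Conclusion.** The point holds as a minor but real flaw in the measurement of a secondary outcome. A cognitively intact right-paretic participant can lose 1 to 3 MMSE points through weakness, and a participant on either side can lose up to 2 more if the paretic hand is the writing hand. Part of any MMSE change could therefore be motor.

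At group level the likely artefact is about 0.03-0.2 points with 1 point at stake and 0.09-0.63 with 3, on the assumed shares and recovery gaps. That is probably below what the trial can detect, on the assumed SD and group size. For an individual, a shift of up to 3 points without cognitive change is possible.

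A reader might go further and conclude that the trial will report a false cognitive benefit of LARA. The document does not support that: it gives no side split, recovery rates or MMSE variability, and the estimated shift is small. The direction of any bias is predictable; its occurrence is not certain. The case for acting rests on the low cost of the change and on the link between the artefact and the treatment target.

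**What to change.** - On the MMSE form, replace the right hand with the non-paretic hand in the paper command.
- Allow folding, writing and copying with the non-paretic hand. Score them on comprehension and content, with credit when weakness alone prevents completion, as NIH Stroke Scale item 1c does. Changing the named hand alone is not enough, because folding may need both hands.
- Record the hand used, and apply the same rule at all three evaluations and at both sites.
- For participants already tested on the printed form, keep the score out of 30 and add a sensitivity analysis without the hand-dependent items. That reduced score also loses comprehension, writing and copying content, so it should supplement the full score and not replace it.

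**Cost.** One form is edited and one field added, with no extra visits or staff. The downside is a small departure from the printed wording and, if enrolment has begun, possibly two form versions in the data. The version used should then be recorded for each assessment.

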After the baseline evaluation, all participants will be randomized into 2 groups: LARA group versus conventional hand and arm exercise program. Randomization will be done through a web-based program.

For LARA group: participants will be fitted for a LARA chair, they will receive a demonstration by a research therapist and be instructed on how to get in/out of the LARA chair, how to propel LARA in a straight line, turns, figure 8 if possible. Participants will also receive training on how to perform arm exercises using a video gaming program. Participants will receive 2 sessions lasting 30 mins each for these training exercises. Participants will begin his/her exercise routine starting the third session. A research therapist will be available to assist but study participants are expected to perform exercise routines by themselves as much as possible. The research therapist will record and keep a log of time spent assisting study participants every day.

If supervising therapists believe LARA participants are skilled enough to drive LARA, participants will begin using LARA to go to therapy appointments and move around ARU by themselves throughout the study.

For control group: participants will receive a demonstration by a research therapist and instructions on how to perform arm/hand exercise programs using towel and table. Towels, tables and an exercise log will be provided. Participants will receive 2 sessions lasting 30 minutes for each training. Participants will begin his/her exercise routine starting the third session. A research therapist will be available to assist but study participants are expected to perform exercise routines by themselves as much as possible. The research therapist will record and keep a log of time spent assisting study participants every day.

Study participants will be compensated with a cash stipend of \$100 for each evaluation. Study participants will receive a maximum total of \$300 from the study.

Time Line of the Study

Visit	Week	Evaluation	Evaluation	Exercise	Training Content
# 1	1	Session #	content	session #	(order to be randomized)
	1	1	Screen		
2	1	T T	All clinical outcomes		
3	1			1	A: LARA or B: Tabletop exercise program
4	1			2	A: LARA or B: Tabletop exercise program
5	1			3	A: LARA or B: Tabletop exercise program
6	1			4	A: LARA or B: Tabletop exercise program
7	1			5	A: LARA or B: Tabletop exercise program
8	2			6	A: LARA or B: Tabletop exercise program
9	2			7	A: LARA or B: Tabletop exercise program

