Answers in **bold** and underlined indicate depression. Although differing sensitivities and specificities have been obtained across studies, for clinical purposes a score > 5 points is suggestive of depression and should warrant a follow-up interview. Scores > 10 are almost always depression.

Subject ID:	
Date:	
Exam#:	

Power Grasp Test

	Trial 1	Trial 2	Trial 3	Average
Grasp (kg) Right				
Grasp (kg) Left				

Grasp

- Displays grip force in pounds (0-200) and kilograms (0-90).
- Isometric; accommodates variable size hands, adjusts to five grip positions (1 ¾" to 3 ¾").
- Set adjustable handle to the desired spacing.
- Rotate the peak hold needle counter-clockwise to 0.
- The patient should be seated with shoulder adducted and neutrally rotated, elbow flexed at 90 degrees, and the forearm in neutral position and wrist between 0-30 degrees dorsiflexion and 0-15 degrees ulnar deviation.
- Let the patient comfortably arrange the instrument in hand. Lightly hold around the readout dial to prevent inadvertent dropping
- Have the patient squeeze with maximum strength.
- 3 trials with 2-3 min. rest period between trials.
- The average of the three trials is recorded.
- Compare the other hand and the normative data. Scores within 2 standard deviations of the mean are considered within normal limits.

Subject ID:	
Date:	
Fxam#:	

Pinch Strength Test

Test	Trial 1	Trial 2	Trial 3	Average
Lateral Pinch (kg)				
Right				
Lateral Pinch (kg)				
Left				

Pinch

- Measures key (Lateral Pinch) strength.
- -Measures in pounds (0-45) or kilograms (0-20).
- -ASHT recommends the following test position: patient should be seated, shoulders adducted and neutrally rotated, elbow flexed at 90 degrees, forearm and wrist in neutral position.
- -Key or lateral pinch: pad of thumb and lateral surface of index finger

Daily Procedures:

- 1. Stroke patients admitted to ARU.
- 2. Screen will be done upon admission (within 1-2 days).
- 3. Baseline evaluation will be performed within 1-3 days after the screening visit. The therapist will see patients in a separate room right outside ARU.
- 4. Randomization occurs after baseline evaluation same day if possible. We will use the web-based formula to randomize patients from both study sites.
- 5. Study participants will be assigned to groups the day after randomization and begin their assigned intervention.

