- 9. If supervising therapists at ARU and research therapist believe LARA participants are skilled enough to drive LARA, participants will begin using LARA to go to therapy appointments and move around ARU by themselves.
- 10. 3 clinical evaluations: baseline, 3-week post therapy or the day before discharge if sooner, 3-month follow up. All clinical evaluations must be completed within 2 days of scheduled dates.
- 11. 3-month follow up is 3 months after baseline evaluation.

Statistical Considerations

Data will be analyzed using modified intention-to-treat analysis. That is, all participants will be included in the analysis if data from the last follow-up assessment is available, regardless of treatment they receive or deviations from protocol. For missing data, we will carry forward the last available value. The effect of treatment on each outcome measure will be assessed using a repeated-measures ANOVA. Follow up analysis will be done using t-tests with Bonferroni corrections, or Wilcoxon rank sum tests if the distributions fail the Lilliefors test for normality. We hypothesize that the participants in the LARA therapy group will have significantly greater reductions in motor impairment measured by FM score than participants in the conventional therapy group. We expect this will be due to the increased dose of therapy LARA provides, and we will include total arm activity (as measured by the wrist-mounted actigraphy) and baseline function as covariates in the analysis. We will compare changes in MAL score, ARAT score, range of motion at the shoulder and elbow, Visual Analog Pain scores, Ashworth Spasticity, and 10 min walk scores using student's t-test or Wilcoxon rank sum tests for non-parametric data. We expect improvements in functional use of the impaired limb (MAL and ARAT) and range of motion but expect no significant differences in pain, spasticity, wheelchair odometer reading, or walking speed. All analyses will be reviewed by our statistical consultant.

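### Site and days since stroke are known at entry but absent from the FM model, which gives up a cheap, probably modest gain in precision; no stratification or blocking is specified

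*Combined protocol and SAP*

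**What the plan says.** - **Population (Background):** "We will recruit 44 individuals with an acute or subacute stroke (3 days to 30 days post stroke"; two centres are named. Inclusion criterion 1 repeats the window: "History of stroke affecting the arm, at least 3 days to 30 days prior to enrollment".
- **Allocation (Methods):** "After the baseline evaluation, all participants will be randomized into 2 groups: LARA group versus conventional hand and arm exercise program", followed by "Randomization will be done through a web-based program".
- **Allocation across sites (Daily Procedures, item 4):** "We will use the web-based formula to randomize patients from both study sites". Randomisation follows the baseline evaluation, on the same day if possible. No stratum, block, minimisation factor or ratio is mentioned.
- **Analysis (Statistical Considerations):** a repeated-measures ANOVA for each outcome, with total arm activity and "baseline function as covariates in the analysis". Arm activity is accumulated after randomisation, so baseline function is the only true baseline covariate. Site and days since stroke appear nowhere in the section.
- **Timing (Daily Procedures, items 10 and 11):** the second evaluation is at 3 weeks or on the day before discharge, whichever is sooner. The last is 3 months after baseline, so it is not timed from the stroke.

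**The concern.** Two people can enter with the same FM score, one at day 3 and one at day 30. They may have different amounts of spontaneous recovery ahead of them. Because follow-up is timed from baseline, their final assessments can also sit up to 27 days apart in time since stroke. Baseline FM alone cannot separate these two people.

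Site may matter through the plan's own procedures. Local discharge practice can bring the second evaluation forward and cut the number of sessions, and supervising therapists help decide who may drive LARA around the unit.

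Both variables are recorded before allocation and cost nothing to use. Leaving them out puts whatever outcome variance they explain into the error term, and leaves the estimate uncorrected for any chance imbalance. With 44 participants and no stated power calculation, precision is scarce. An unadjusted imbalance would also be awkward to defend when the results are read.

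**Working it through.** The sample size cannot be reproduced, because the plan gives no alpha, power, effect size, SD, allocation ratio or dropout rate. The checks below therefore measure what the omission could cost.

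**Inputs from the plan:** N = 44; two sites; entry at 3 to 30 days; one baseline covariate.

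**Assumptions:** 1:1 allocation (22 per arm), no dropout, two-sided alpha 0.05, and baseline function taken to mean baseline FM. The split between sites, the spread of days and the variance explained are not given, so ranges are shown.

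**1. Imbalance in days since stroke.** SE of the arm difference = SD × √(2/22); the probability of a gap over 3 days is 2 × (1 − Φ(3/SE)).

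| SD of days (assumed) | SE | P(gap > 3 days) |
|---|---|---|
| 4 | 1.21 | 1% |
| 6 | 1.81 | 10% |
| 7.8 (uniform over 3–30: 27/√12 = 7.79) | 2.35 | 20% |

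**2. Imbalance in site.** With arms fixed at 22/22, the number from one site in one arm is hypergeometric. The probability that the arms differ by 20 percentage points or more in site share is 13% for sites of 22/22 (a 14:8 split or worse), 20% for 15/29 and 16% for 11/33. If allocation is simple instead, simulation gives 18%, 18% and 14%.

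**3. What an imbalance in days would do.** Suppose days explain 10–20% of residual variance. A 3-day gap at SD 7.79 is 3/7.79 = 0.385 SD of days. It shifts the arm difference by √0.10 × 0.385 = 0.12 to √0.20 × 0.385 = 0.17 outcome SD. The SE of the arm difference is √(2/22) = 0.30 SD, so the shift is about 0.4–0.6 of a standard error. The difference detectable with 80% power is (1.96 + 0.842) × 0.3015 = 0.845 SD.

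**4. Gain from adjusting.** Let R² be the extra residual variance that site and days explain beyond baseline FM. The SE falls by 1 − √(1 − R²), and the equivalent unadjusted total is 44/(1 − R²). Power uses the normal approximation at a true difference of 0.845 SD.

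| Extra R² (assumed) | SE reduction | Equivalent N | Power |
|---|---|---|---|
| 0 | 0% | 44 | 80% |
| 0.05 | 2.5% | 46 | 82% |
| 0.10 | 5.1% | 49 | 84% |
| 0.20 | 10.6% | 55 | 88% |

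**5. Cost if the covariates explain nothing.** On the t distribution, moving from 40 to 38 residual degrees of freedom takes power from 78.1% to 78.0%, a loss of about 0.1 percentage point.

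**6. What stratification adds once site is in the model.** With a 14:8 split at equal sites, the arm–site correlation is (14 − 8)/22 = 0.273. The SE is inflated by 1/√(1 − 0.273²) = 1.039, or 3.9%, and a split that bad or worse has probability 13%. Most of the benefit therefore comes from the covariates.

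**The case against.** Several points on the other side are sound.

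- **Silence is not exclusion.** A reader might infer that the randomisation is unstratified or simple. The plan says only that a web-based program or formula is used for both sites; such a system can stratify and block without this being written down. What stands is that no method is specified. The simple-allocation figures above are conditional for that reason.
- **Imbalance is not bias.** A reader might infer that unequal days or sites would invalidate the comparison. Under valid randomisation the test's error rate already allows for chance imbalance, and even a 3-day gap moves the estimate by only about half a standard error on the assumptions used. The cost is precision and credibility.
- **The 20% figure uses a wide spread.** It needs entry times spread evenly across the window. Screening within 1–2 days of admission, and baseline 1–3 days later, may cluster them; at an SD of 4 the probability is 1%.
- **The variance explained is assumed.** The plan gives no site effect or time effect, baseline function may already absorb part of the time effect, and the same written procedures apply to both sites. At an extra R² of 0.05 the gain is about two points of power.
- **Severity is already handled.** With baseline function in the model, stratifying by FM is a preference, and site by two FM levels would give four strata averaging 11 people.

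All of this limits the size of the gain. None of it is a reason to leave out two baseline variables that are already known and cost almost nothing to include.

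**Conclusion.** The point holds as a low-priority improvement. The FM analysis uses one baseline covariate and omits two others that are known at entry and plausibly prognostic. The likely loss is modest: an SE about 2.5–11% larger than it need be if site and days explain an extra 5–20% of residual variance. That range is assumed and nothing in the documents fixes it. A gap of more than 3 days between arms is possible but not the expected result (1–20% of trials, depending on the spread assumed).

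The documents do not support saying that the trial is unstratified, that the treatment comparison is biased, or that an FM stratum is needed. The missing description of the allocation method is a reporting gap, secondary to the covariates.

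**What to change.** **Main change, in Statistical Considerations:** prespecify that the primary FM model includes baseline FM, site and days since stroke at enrolment as covariates, and name baseline FM as the score meant by baseline function. This is one sentence. It can be made after enrolment has begun, provided it is fixed before any unblinded analysis. The cost is two model degrees of freedom.

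**Secondary change, in Methods and Daily Procedures item 4:** state the allocation ratio and whether the web program uses blocks or strata. If it already stratifies by site, say so; the site term in the model then matches the design. If it does not, set permuted blocks stratified by site for participants still to be randomised. With small blocks this holds the within-site difference in arm sizes to at most half a block. The cost is a program setting and a possible incomplete block at each site. No FM stratum is needed.
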